Seven-point blood glucose profiles (measuring glucose via finger stick, at the following times of day: before each meal, 2 hours after each meal, and at bedtime) will be performed for periods of three consecutive days. During the Lead-In Period, subjects will record their seven-point blood glucose (BG) profile over a single period of three consecutive days, prior to the Baseline Visit for subjects enrolled in Part A, or prior to the Day 1 Visit for subjects enrolled in Part B. During the 12 week Dosing Period and 12 week Follow-up Period, seven-point BG profiles will be performed over the three consecutive days following Dose 4 (Study Days 23 – 25), Dose 8 (Study Days 51 – 53), and Dose 12 (Study Days 79 – 81), and during Weeks 16 and 20 of the Follow-up Period.

Subjects will be provided with a blood ketone meter and blood ketone test strips in order to measure blood ketone readings via finger-stick method. For subjects enrolled in Part A only, blood ketone readings will be performed in the morning and collected by the subject while in a fasted state, prior to the subject's morning meal. During the 12-Week Dosing Period (starting on Day 1 and continuing through the completion of Week 12) the blood ketone readings will be performed 3 days a week – on an alternate day basis starting on Day 1 (e.g. Week 1: Study Days 1, 3, 5 or on Mondays, Wednesdays, and Fridays), and once weekly during the 12-Week Follow-up Period. Subjects will be instructed to contact the investigator if they have positive ketones and blood sugars > 300 mg/dL. Subjects enrolled in Part B will also be provided with a blood ketone meter and blood ketone test strips to be used as needed, however, there is no

required collection schedule. Subjects in Part B will be advised to perform blood ketone readings via finger-stick method when they feel ill, or symptomatic of ketoacidosis, or as instructed by the investigator.

The Type 1 – Diabetes Distress Scale (T1-DDS) and WHO-5 Well-Being Index scales ([Appendix D](#)) will be provided to the subject at the beginning of the following study visits: Baseline Visit and Day 85 and Day 161(EOS) visits.

PK blood samples and fasting plasma glucose samples will be collected as described in the Schedule of Assessments. For those samples that are scheduled for collection on days when study drug is administered, those samples should be collected pre-dose.

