Seven-point blood glucose profiles (measuring glucose via finger stick, at the following times of day: before each meal, 2 hours after each meal, and at bedtime) will be performed for periods of three consecutive days. During the Lead-In Period, subjects will record their seven-point blood glucose (BG) profile over a single period of 3 consecutive days either, prior to the Baseline Visit (subjects participating in Part A) or prior to the Day 1 Visit (subjects participating in Part B). During the 12 Week Dosing Period and 12 Week Follow-up Period, seven-point BG profiles will be performed over the three consecutive days following Dose 4 (Study Days 23 – 25), Dose 8 (Study Days 51 – 53), and Dose 12 (Study Days 79 – 81), and during Weeks 16 and 20 of the Follow-up Period.

Ketone Finger-Stick

Subjects will be provided with a blood ketone meter and blood ketone test strips in order to measure blood ketone readings via finger-stick method. For subjects in Part A only, blood ketone readings will be performed in the morning and collected by the subject while in a fasted state, prior to the subject's morning meal. During the 12-Week Dosing Period (starting on Day 1 and continuing through the completion of Week 12) the blood ketone readings will be performed 3 days a week – on an alternate day basis starting on Day 1 (e.g. Week 1: Study days 1, 3, 5 or on Mondays, Wednesdays, and Fridays), and once weekly during the 12-Week Follow-up Period. Subjects will be instructed to contact the investigator if they have positive ketones and blood sugars > 300mg/dL. Subjects enrolled in Part B will also be provided with a blood ketone meter and blood ketone test strips to be used as needed, however, there is no required collection schedule. Subjects in Part B will be advised to perform blood ketone readings via finger-stick method when they feel ill, or symptomatic of ketoacidosis, or as instructed by the investigator.

The blood ketone results will be automatically recorded in the combination blood glucose /blood ketone meter. **Please Note:** Data from the blood glucose / blood ketone meter will need to be collected and reviewed by the investigator and/or study staff at each study visit.

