Readings will be made by gently inserting the test strip into the meter, after which the subject will apply a small drop of blood from the finger to the white target area at the end of the test strip. The blood is then drawn into the test strip, at which time the blood ketone value will be displayed on the blood ketone test meter. Additionally, serum ketones and free

fatty acids will be measured during each weekly visit during the treatment period, as outlined in the Schedule of Assessments ([Appendix A](#)).

Quality of Life (QOL) Questionnaire

The Type 1 – Diabetes Distress Scale (T1-DDS) and WHO-5 Well-Being Index scales ([Appendix D](#)) will be provided to the subject at the beginning of the following study visits: Overnight Baseline Visit and Days 85 and 161(EOS) visits.

The T1-DDS is a validated survey instrument that assesses diabetes-related emotional distress and includes 28 items. Thinking back over the past month, the subject will be asked to indicate the degree to which each of the items may have been a problem.

The WHO-5 Well-Being Index scale includes five statements in which the subject will need to rate based on how the subject has been feeling over the last two weeks.

Blood Volume

It is anticipated that subjects enrolled in this study will agree to provide whole blood for safety, PK, and PD assessments during their participation in this study as listed in [Table 7-1](#):

Table 7-1: Total Blood Volume for samples collected prior to Protocol Amendment #1, for subjects participating in Part A

Procedure	Volume per Collection (mL)	Number of Collections	Total Volume (mL)
Safety (chemistry + hematology)	5	9	45
Fasting Plasma Glucose	2	15	30
Fasting Lipid Panel	5	9	45
Serum PK sample collection	4	6	24
Serum FSH levels (women only) ^Φ	5	1	5 ^Φ
HbA1c	6	4	24
Plasma Glucose via YSI	0.75	27	20
MMTT (glucose & insulin)	40	3	120
GLP-1 (active & total), Glucagon, Plasma insulin and C-peptide	4	6	24
Anti-REMD-477 Ab sample collection *	10 (first) / 5	3	20
Exploratory biomarker collection	30	3	90
Serum Ketones & free fatty acids	1.5	15	22.5
TOTAL **			464.5 469.5^Φ

* First collection is 10 mL, subsequent collections are 5 mL.

** Volume to be collected over approximately 238 days.

**Table 7-2: Total Blood Volume for samples collected under Protocol Amendment #1,
 for subjects participating in Part A**

Procedure	Volume per Collection (mL)	Number of Collections	Total Volume (mL)
Safety (chemistry + hematology)	5	9	45

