Fasting Plasma Glucose	2	15	30
Fasting Lipid Panel	5	9	45
Serum PK sample collection	4	6	24
Serum FSH levels (women only) ^Φ	5	1	5 ^Φ
HbA1c	6	4	24
Plasma Glucose via YSI	NA	NA	NA
MMTT (glucose & insulin)	40	2	80
GLP-1 (active & total), Glucagon, Plasma insulin and C-peptide	4	6	24
Anti-REMD-477 Ab sample collection *	10 (first) / 5	3	20
Exploratory biomarker collection	30	3	90
Serum Ketones & free fatty acids	1.5	15	22.5
TOTAL**			404.5 409.5^Φ

* First collection is 10 mL, subsequent collections are 5 mL.

** Volume to be collected over approximately 238 days.

Table 7-3: Total Blood Volume for samples collected under Protocol Amendment #2, for subjects participating in Part B

Procedure	Volume per Collection (mL)	Number of Collections	Total Volume (mL)
Safety (chemistry + hematology)	5	9	45
Fasting Plasma Glucose	2	15	30
Fasting Lipid Panel	5	9	45
Serum PK sample collection	4	6	24
Serum FSH levels (women only) ^Φ	5	1	5 ^Φ
HbA1c	6	5	30
GLP-1 (active & total), Glucagon, Plasma insulin and C-peptide	4	6	24
Anti-REMD-477 Ab sample collection *	10 (first) / 5	3	20
Exploratory biomarker collection	30	3	90
Serum Ketones & free fatty acids	1.5	15	22.5
Liver Injury Biomarkers	10	5	50
TOTAL**			380.5 385.5^Φ

* First collection is 10 mL, subsequent collections are 5 mL.

** Volume to be collected over approximately 224 days.

Laboratory Safety Tests

Blood and urine samples for laboratory safety tests (clinical chemistry, hematology, and urinalysis) will be collected according to the Schedule of Assessments ([Appendix A](#)).

The date and time of blood and urine collection will be recorded in the subject's source documentation. The tests will be analyzed using standard procedures. White blood cell differentials will be reported in absolute counts.

All laboratory tests must be reviewed by the Principal Investigator or qualified designee prior to the subject receiving each dose. Additional safety laboratory assessments may be performed if clinically indicated.

The following analytes will be tested:

Chemistry

Albumin	Blood urea nitrogen (BUN)
Calcium	Chloride
Glucose	Phosphorus
Potassium	Serum creatinine
Magnesium	Sodium
Bicarbonate	Uric acid
Aspartate aminotransferase (AST)	Alanine aminotransferase (ALT)
Cholesterol	Lactate dehydrogenase (LDH)
Alkaline phosphatase (ALP)	Total bilirubin
Total protein	Direct bilirubin
HDL, LDL, Triglycerides	Total globulin

Hematology

Red blood cells (RBC)
Hemoglobin (Hgb)
Hematocrit (Hct)
Mean corpuscular volume (MCV)

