- i. Subjects will be given insulin usage diaries during the Lead-in Period and at the beginning of Weeks 1 through 4, 8, 12, 16, and 20. For both weeks of the Lead-in Period and Weeks 1 through 4, daily insulin use (short-acting, long-acting, and infusional as applicable) will be collected over seven days. For Weeks 8, 12, 16, and 20, daily insulin will be collected over a period of 3 consecutive days within that respective week.
- j. Blood ketones will be measured in the morning (prior to the subject's morning meal) 3 days a week – on an alternate day basis (e.g. Week 1: Study days 1, 3, and 5 or on Mondays, Wednesday, and Fridays) during the 12-Week Dosing Period (starting on Day 1 and continuing through the completion of Week 12), and once weekly throughout the Follow-up Period & EOS (Day 85 through Day 162) via finger-stick (strips for finger-stick measurement will be provided to the subjects). Subjects will be instructed to contact the investigator if they have positive ketones.
- k. The *WHO-5 Well-Being Index & T1-DDS* QOL Questionnaires will be completed by the subjects at the OBV, Day 84, and Day 161.
- l. No longer applicable for ongoing or newly enrolled subjects at time of Protocol Amendment #1.

Schedule of Assessments – Part A

Study Period (or Dose#)	Dose 9	Dose 10	Dose 11	Dose 12	Follow-up Period			EOS					
Study Week	9	10	11	12	13 ^m	16	20	24 ^m					
Study Day	57 ± 1	64 ± 1	71 ± 1	78 ± 1	84 ± 2	85 ± 2	106 ± 2	134 ± 2	161 ± 2	162 ± 2			
Informed consent													
Medical History ^a													
Physical examination					X				X				
Body weight	X				X	X	X		X				
Urine pregnancy test (women); FSH ^g	X				X				X				
Urine drug/alcohol test									X				
12-lead ECG ^b	X		X			X			X				
Vitals (BP, RR, HR, T) ^c	X	X	X	X	X	X	X	X	X				
Chemistry, Hematology, Lipid Panel, and Urinalysis	X					X			X				
Fasting (\geq 8-hr) plasma glucose ^e	X	X	X	X		X			X				
Serum Ketones & Free Fatty Acids	X	X	X	X		X	X						
Study Drug SC Administration	X	X	X	X									
Seven-point blood glucose profile ^d				X			X	X					
Unblinded Continuous Glucose Monitoring (CGM) ^h	↔												
Daily (or Weekly) Ketone finger-stick ^j	X	X	X	X		X	X						
Daily insulin usage diary ⁱ				X		X	X						
Hourly plasma glucose via YSI ^e					X ¹	X ¹		X ¹	X ¹				
Mixed Meal Tolerance Test (MMTT) ^e						X			X ¹				
Arginine Challenge Test ^e						X ¹			X ¹				
HbA1c						X			X				
Insulin, C-peptide, GLP-1, and Glucagon ^{e,f}	X					X	X		X				

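### The Part A ketone contact rule is stated two ways, with a glucose condition in the synopsis and Section 7 and without one in the Schedule footnote

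*Protocol*

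**What the plan says.** The contact rule appears five times in the current protocol, in two forms.

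- **Ketones and glucose.** Section 7 states it twice, under Throughout the Study and under Ketone Finger-Stick: "Subjects will be instructed to contact the investigator if they have positive ketones and blood sugars > 300mg/dL". The synopsis, under Throughout the Study, has the same rule: "Subjects will be instructed to contact the investigator if they have positive ketones and blood sugars > 300 mg/dL".
- **Ketones alone.** Footnote j of the Part A Schedule of Assessments (Appendix A), printed under both halves of the table, reads: "Subjects will be instructed to contact the investigator if they have positive ketones". The sentence ends there. It states no glucose condition and does not refer back to Section 7.

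Scheduled home testing is for Part A only: three mornings a week, fasted, during the 12 dosing weeks, then "once weekly during the 12-Week Follow-up Period" (footnote j: "once weekly throughout the Follow-up Period & EOS (Day 85 through Day 162) via finger-stick"). Part B subjects get a meter for use as needed, and the Part B schedule has no ketone finger-stick row.

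The meter data "will need to be collected and reviewed by the investigator and/or study staff at each study visit" (Section 7, Ketone Finger-Stick). Serum ketones are drawn as well; Section 7 says that these and free "fatty acids will be measured during each weekly visit during the treatment period".

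**The concern.** The two forms give different instructions to a subject with positive ketones and glucose of 300 mg/dL or less. This is not a remote corner of the data. Scheduled readings are taken before breakfast, and Section 7 tells subjects to titrate basal insulin to a pre-breakfast glucose of 80-120 mg/dL. For a subject at target, any positive scheduled reading falls where the two rules disagree.

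At stake is how consistently sites tell subjects when to report ketosis. If a site trains from the body text, such a reading need not be phoned in, and staff may first see it when the meter is reviewed at the next visit.

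**Working it through.** The plan gives no figure to reproduce. The check compares the texts and then works out how long an unreported reading could wait.

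**Step 1. The two rules by case.**

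- Ketones positive, glucose above 300 mg/dL: call under both forms.
- Ketones positive, glucose at or below 300 mg/dL: call under footnote j, no call required by the synopsis or Section 7.
- Ketones not positive: no call under either.

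Three statements carry the glucose condition and two do not. Footnote j covers every case that the body text covers, so following it satisfies both. None of the five places gives a numeric cut-off for a positive reading.

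**Step 2. Which text governs.** Section 7 opens by asking sites to make every effort to perform procedures as the Schedule indicates, and the synopsis says study procedures are shown in Appendix A. Both lean towards footnote j. Neither says that the Schedule prevails where texts differ.

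**Step 3. Readings per Part A subject.**

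- Dosing: 3 per week x 12 weeks = 36.
- Follow-up, weekly from Day 85 to Day 162: (162 - 85)/7 + 1 = 12.
- Total: 36 + 12 = 48, for a planned Part A size of about 75.

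**Step 4. Longest wait to the next meter review.** Visit days and windows come from Appendix A, Part A (plus or minus 1 day for dosing visits after Day 1, plus or minus 2 days from Day 85).

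- Between dosing visits: 7 days; with windows 7 + 1 + 1 = 9.
- Day 78 to Day 85: 7 days; with windows 87 - 77 = 10.
- Day 85 to Day 106: 21 days; with windows 108 - 83 = 25.
- Day 106 to Day 134: 28 days; with windows 136 - 104 = 32.
- Day 134 to Day 162: 28 days; with windows 164 - 132 = 32.

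These are upper limits, for a reading taken just after a visit. The last dose is on Day 78, so the 21-day gap opens 85 - 78 = 7 days after it, and the 28-day gaps open 106 - 78 = 28 and 134 - 78 = 56 days after it.

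**Step 5. What else could catch the reading.**

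- Phone calls 3-4 days after Doses 1 and 2 cover insulin use and glucose control. Ketones are not named.
- Part A CGM is unblinded and serves safety monitoring. It shows glucose, not ketones. For subjects ongoing or newly enrolled at Amendment #2 it stops at Day 85.
- Table 7-2 lists 15 collections for "Serum Ketones & free fatty acids". The baseline visit, Day 1 pre-dose and Doses 2 to 12 account for 1 + 1 + 11 = 13, leaving 2 in follow-up. All take place at visits.
- Adverse events are collected throughout when reported, so a subject with symptoms has another route.

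**The case against.** The best case against is that this is a loose footnote with little consequence. Footnote j may be shorthand for the body rule, since it also leaves out the fasted state. A site can obey both forms by following the footnote, and Section 7 already points sites to the Schedule. The instructions actually handed to subjects are not in these documents, so divergent practice is possible but not shown. The long follow-up gaps come from visit spacing and would exist under any rule. The majority wording, including the section devoted to the finger-stick test, has the glucose condition, and which trigger is clinically right is the sponsor's decision.

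Much of this stands. A reader might infer that sites have no guidance on which text to follow; that goes too far, given the general direction to the Schedule. A reader might also infer that positive readings would go unseen for a month. The documents support that only as a worst case in off-drug follow-up, with other routes of detection in place.

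What does not fall away is the conflict itself. A general pointer to the Schedule is not a precedence clause, and nothing in footnote j signals that it is an abbreviation. If the sponsor did intend the glucose condition, the footnote is the text in error and still needs correcting.

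**Conclusion.** The inconsistency is real, confined to Part A, and worth correcting as a matter of subject safety. It concerns positive readings at or below 300 mg/dL among about 48 scheduled readings per subject. The possible delay is about 7 days in dosing (9 with windows, 10 between Days 78 and 85) and at worst 21 to 28 days (25 to 32 with windows) in follow-up, partly mitigated as described above.

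The size rests on three assumptions: some sites use the body text, the subject does not call for another reason, and the meter review is the first time staff see the reading. The documents give neither the rate of positive readings at or below 300 mg/dL nor the number of Part A subjects whom a correction could still reach; 75 is the planned total.

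Two further inferences are unsupported. The conflict does not threaten the trial's results: SAP 10.3.4.9 only lists finger-stick ketones, and the individual stopping rules in Protocol Section 6 name no ketone criterion. Nor does it imply that the drug causes ketosis; the protocol's background section links unrestrained glucagon action to ketone production, which if anything points the other way.

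**What to change.** State one rule in all five places: the synopsis, both statements in Section 7, and both printings of footnote j. The broader trigger is preferable because it satisfies both present versions and removes no call now required. Suggested wording:

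*A Part A subject must call the investigator after any blood ketone reading at or above the supplied meter's stated cut-off for positive, whatever the blood glucose.*

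The cut-off belongs in the rule itself, because without the glucose condition the whole trigger rests on the word positive. If the sponsor prefers to keep the 300 mg/dL condition, footnote j should be changed to match and the cut-off still stated.

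Notify sites and ongoing Part A subjects of the rule. The cost is five wording changes, that notice, and some extra calls for fasting ketosis at lower glucose, whose number cannot be computed from the documents. No analysis needs to change.

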Following single SC administration of REMD-477 in healthy subjects, REMD-477 was slowly absorbed, with C_{max} observed at median T_{max} of 4 to 5 days post-dose. Exposure, as assessed by C_{max} and AUC_{0-inf} , increased more than dose-proportionally between the 0.3- and 2.5 mg/kg dose range. The effective half-life was approximately 2 weeks across dose groups. Mean residence time (MRT_{0-t}) increased with increasing dose and reached 317 ± 63 hours at 2.5 mg/kg SC. Following IV administration of REMD-477 at 0.3 mg/kg, the C_{max} was between the C_{max} values from the 1 and 2.5 mg/kg SC cohorts. Exposure based on AUC for the 0.3 mg/kg SC dose group was approximately 25% of that achieved for the corresponding IV dose group.

Phase-1 Study T1DM: R477-101

Protocol R477-101 is a randomized, placebo-controlled, double-blind study to evaluate safety, tolerability and pharmacodynamics of REMD-477 in subjects who have Type 1 diabetes and are currently receiving insulin treatment. This proof of concept study evaluated whether glucagon receptor blockade using a single dose 70 mg SC of REMD-477 could decrease insulin requirements and improve glucose homeostasis versus placebo in patients with Type 1 diabetes. The study was completed in January, 2017.

Patients were admitted to an inpatient facility and evaluated over the course of 5 days. Insulin requirements to achieve tight glycemic control was determined on Day 1. On Day 2, insulin infusions were reduced to increase glucose levels to 250-300 mg/dL and REMD-477 or placebo was injected. On Days 3 and 4, insulin was then adjusted to maintain glycemic control similar to that achieved on Day 1. Continuous glucose monitoring was conducted throughout the study to evaluate glucose fluctuation, average glucose concentration, and percentage of time in range (70-180 mg/dL), percentage of time with low glucose concentrations (<70 mg/dL), and percentage of time with high glucose concentrations (>180 mg/dL).

A total of 21 patients were enrolled. Based on preliminary review of safety data review in January 2017, a single dose of 70 mg SC REMD-477 was safe and well-tolerated. There were

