no significant drug related adverse events. No deaths, dose limiting toxicities or withdrawals due to adverse events have been reported. No notable changes in ECG, safety lab tests, or vital signs were reported. One patient whose treatment assignment remains blinded experienced an increase in ALT that was less than 1.6 times the upper limit of the laboratory normal on Days 22 and 50 after a single SC injection. There was no corresponding increase in bilirubin or alkaline phosphatase. The elevation occurred 21 and 49 days after administration of treatment which is not consistent with previous observations for liver enzyme increases in both healthy subjects and Type 2 diabetics which usually occur between 4-14 days after drug administration. No severe hypoglycemia was reported in the study patients.

An interim analysis of the first 17 subjects found REMD-477 treatment reduced daily insulin use by 32% (4.2%, 60%) vs. placebo on Day 4 ($p=0.027$). Average daily glucose assessed by CGM was 19 mg/dL (6.2, 31; $p=0.006$), and 26 mg/dL (8.2, 45; $p=0.008$) lower in the REMD-477 group than in the placebo group at Weeks 2 and 3 after treatment, respectively. Glucose time-in-range (70-180 mg/dL) for REMD-477 was 9.5% (2.7%, 16%; $p=0.009$) and 13% (1.9%, 25%; $p=0.026$) greater in the REMD-477 group than in the placebo group during Weeks 2 and 3 after treatment, respectively.

Phase-1b-2a Study T2DM: R477-201

Protocol R477-201 is a randomized, placebo-controlled, double-blind, dose escalation study to evaluate safety, tolerability, PK and PD of single and repeated SC doses of REMD-477 in Type 2 diabetic subjects. The ongoing study includes a dose escalation phase (Part A) followed by an adaptive dose cohort phase (Part B) and two additional cohorts testing REMD-477 in combination with metformin (Part C).

In Parts A and B, approximately 72 subjects will be enrolled with Type 2 diabetes who are either treatment-naïve, controlled with diet and exercise or treated with oral antidiabetic medications. As of February 2017, 60 of subjects have been enrolled across 5 dose cohorts at dose levels of 14 mg, 28 mg, 35 mg, 42 mg, and 70 mg. Each cohort included 9 patients treated with REMD-477 and 3 treated with placebo. Patient received a single SC injection and 28 day observation followed by 8 weekly SC injections.

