The proposed dose design for the current study is for subjects to be randomized in a 1:1:1 fashion into one of three treatment groups (placebo, 35 mg REMD-477, or 70 mg REMD-477). Subjects will receive once weekly SC injections of investigational product for 12 weeks and be followed for an additional 12 weeks during washout in the Safety Follow-up Period. In

the subjects with Type 2 diabetes, increasing dose and exposure from 14 mg to 42 mg was associated with reduction in HbA1c. Based on available unblinded interim data, the maximum HbA1c reduction of 1% was achieved at 42 mg after 8 repeated weekly doses. In a blinded evaluation of the 70 mg cohort safety data, ALT increases were observed in a greater number of subjects relative to previous lower dose cohorts. In contrast, a single SC dose of 70 mg REMD-477 was not associated with significant increases in ALT in subjects with Type 1 diabetes. Only one subject who received blinded treatment had elevated ALT that were up to 1.6x ULN.

After a single dose of 70 mg of REMD-477 in subjects with Type 1 diabetes, significant reductions in insulin, average glucose, and time in range after CGM were observed. With repeated weekly dosing, substantial (10-30x) accumulation of REMD-477 is expected.

Based on the above findings, dose levels of 35 mg and 70 mg administered once weekly by SC injection over 12 weeks are being proposed. At these dose levels, significant improvements in glycemic control and reduction in insulin requirements are expected after multiple dosing. In addition, minimal to no transaminase elevations are expected based on the findings in Type 1 diabetics after a single 70 mg dose and the manageable transaminase elevations in Type 2 diabetics.

Hypothesis

Multiple doses of REMD-477 will significantly decrease daily insulin use versus placebo treatment at Week 12.

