Blood samples for biomarker purposes will be collected pre-dose on Day 1, Day 85, and Day 162 (EOS Visit). These samples may be used in future analyses in an effort to identify novel biomarkers for diabetes and glucagon-related pathways.

Liver Injury Biomarker Collection

For subjects enrolled in Part B, blood samples to measure biomarkers of liver injury will be collected pre-dose on Day 1, Day 29, Day 57, Day 85, and Day 106. Sample collection, serum processing, and shipping instructions will be provided in a separate lab manual.

These biomarkers will include but are not limited to cytokeratin 18 (CK-18) M65, CK-18 M30, high mobility group protein B1 (HMGB1), and glutamate dehydrogenase.

Magnetic Resonance Imaging – Proton Density Fat Fraction (MRI-PDFF)

For a subset of subjects in Part B only who consent to the procedure, liver MRI-PDFF will be performed prior to dosing on Day 1 (or up to 7 days prior to the Day 1 visit, after all other inclusion and exclusion criteria have been met) and on Day 85 (+/- 2 days) of Week 13.

MRI-PDFF will only be performed at centers with equipment and software capable of conducting the scans. Subjects for whom an MRI is contraindicated (e.g., including but not limited to artificial heart valves or pacemakers), will be not enrolled to this sub-study.

Baseline and post-treatment MRI-PDFF will be performed to assess changes in liver fat content. This technique utilizes a gradient echo sequence with low flip angle to minimize the T_1 bias, and it acquires multiple echoes at echo times at which fat and water signals are nominally in-phase or out-of-phase relative to each other. Data obtained at each of the echo times are passed to a nonlinear least-squares fitting algorithm that estimates and corrects T_2^* effects, models the fat signal as a superposition of multiple frequency components, and estimates fat and water proton densities from which the fat content is calculated.

Imaging PDFF will be recorded in regions of interest (ROIs) 300 to 400 mm² in area placed on the PDFF parametric maps, avoiding blood vessels, bile ducts, and artifacts. To assess longitudinal changes in fat content, multiple co-localized ROIs will be placed in each of the liver segments on the baseline and follow-up MRI exams.

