- h. Subjects will be given insulin usage diaries during the Lead-in Period and at the beginning of Weeks 1 through 4, 8, 12, 16, and 20. For one week of the Lead-in Period and Weeks 1 through 4, daily insulin use (short-acting, long-acting, and infusional as applicable) will be collected over seven days. For Weeks 8, 12, 16, and 20, daily insulin will be collected over a period of 3 consecutive days within that respective week.
- i. The *WHO-5 Well-Being Index & T1-DDS QOL* Questionnaires will be completed by the subjects at the Baseline, Day 84, and Day 161.
- j. Both the Liver MRI and FibroScan Baseline Assessments may be performed up to 7 days before the Day 1 Visit, after all other inclusion and exclusion criteria have been met.

Schedule of Assessments – Part B

Study Period (or Dose#)	Dose 9	Dose 10	Dose 11	Dose 12	Follow-up Period			EOS
Study Week	9	10	11	12	13	16	20	24
Study Day	57 ± 1	64 ± 1	71 ± 1	78 ± 1	85 ± 2	106 ± 2	134 ± 2	162 ± 2
Informed consent								
Medical History ^a								
Physical examination					X			X
Body weight	X				X	X	X	X
Urine pregnancy test (women); FSH ^f	X				X			X
Urine drug/alcohol test								X
12-lead ECG ^b	X		X		X			X
Vitals (BP, RR, HR, T) ^c	X	X	X	X	X	X	X	X
Chemistry, Hematology, Lipid Panel, and Urinalysis ^e	X				X			X
Fasting (\geq 8-hr) plasma glucose ^e	X	X	X	X	X			X
Serum Ketones & Free Fatty Acids ^e	X	X	X	X		X	X	
Study Drug SC Administration	X	X	X	X				
Seven-point blood glucose profile ^d				X		X	X	
Blinded Continuous Glucose Monitoring (CGM) ^g				X				
Daily insulin usage diary ^h				X		X	X	
HbA1c					X			X
Insulin, C-peptide, GLP-1, and Glucagon ^e	X				X	X		X
Serum PK sample collection ^e	X				X	X		
Anti-REMD-477 Ab sample collection ^e					X			X
Exploratory biomarker collection ^e					X			X
Liver Injury Biomarkers ^e	X				X	X		
Liver MRI/FibroScan ^j					X			
QOL Questionnaires ⁱ					X			X
Con-Med monitoring	↔							→
Adverse event monitoring	↔							→

Footnote Key:

- a. Medical history includes significant past medical events (e.g. prior hospitalizations or surgeries), a review of diabetes history and glycemic control, and any concurrent medical illnesses.
- b. After the Screening Visit, 12-lead ECG to be performed in triplicate, approximately 1 min apart. When ECG and blood sample collection occur at the same time, ECGs should be performed before blood samples are drawn.
- c. Vital signs include blood pressure, respiratory rate, heart rate, and oral temperature.

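### After Day 85 no ALT, AST, ALP or bilirubin is scheduled until Week 24 in either Part, and Day 106 is the only Part B liver-biomarker draw without same-visit transaminases

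*Protocol*

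**What the plan says.** Protocol Section 7 (Laboratory Safety Tests) lists AST, ALT, alkaline phosphatase, and total and direct bilirubin under Chemistry. It leaves the timing to Appendix A: "Blood and urine samples for laboratory safety tests (clinical chemistry, hematology, and urinalysis) will be collected according to the Schedule of Assessments". In Appendix A the row is "Chemistry, Hematology, Lipid Panel, and Urinalysis". On the follow-up pages of both Parts it is marked at Day 85 and at the Week 24 visit, and is blank at Days 106 and 134.

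For Part B subjects, Section 7 (Liver Injury Biomarker Collection) states: "blood samples to measure biomarkers of liver injury will be collected pre-dose on Day 1, Day 29, Day 57, Day 85, and Day 106". The named markers are two CK-18 fragments, HMGB1 and glutamate dehydrogenase. The list is open-ended, but ALT, AST and bilirubin are not on it.

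On exposure, the first-in-human summary in Section 2 says: "The effective half-life was approximately 2 weeks across dose groups". The type 2 diabetes study gives about 1 week. Section 7 schedules a drug concentration sample on Day 106 in both Parts. On timing, Section 2 (R477-101) says that liver enzyme increases "usually occur between 4-14 days after drug administration".

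SAP 10.4.2 tabulates ALT and AST above 3x, 5x and 10x ULN, both as a post-dose maximum and by time point. SAP 10.1.2 excludes unscheduled laboratory readings from all summaries, except as a baseline value.

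**The concern.** Raised ALT is the one notable laboratory finding that Section 2 reports for repeated dosing. In the type 2 study, rises up to 3x ULN occurred in 7 of 12 patients in the 70 mg cohort, with one isolated value of 18x ULN. This trial gives 70 mg weekly for 12 weeks in one arm, and its reassurance for type 1 diabetes comes from a single dose.

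The 12-week safety follow-up therefore ought to show what transaminases do as drug washes out. As scheduled, it sees them one week after the last dose and then at the end. In Part B the plan does look at the liver on Day 106, but without the standard enzymes at that visit. The Part B FibroScan trigger (first AST or ALT above 3x ULN) also cannot be met from any scheduled draw in the interval.

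**Working it through.** **1. Are the blanks real?** The row in Tables 7-1 to 7-3 that begins "Safety (chemistry + hematology" gives 9 collections in each table. Counting the Appendix A marks:
- Part B: screening, baseline, Days 8, 15, 29, 43, 57, 85, 162 = 9.
- Part A: screening, baseline, Days 8, 15, 29, 43, 57, 85, Week 24 = 9. The Part A follow-up marks sit in the same positions as the antibody row, which Section 7 dates to Days 85 and 162.

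The stated 9 is used up without Day 106 or Day 134. The Table 7-3 total also reproduces: 45 + 30 + 45 + 24 + 30 + 24 + 20 + 90 + 22.5 + 50 = 380.5 mL.

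**2. Length of the gap.** 162 − 85 = 77 days, or 73 to 81 with the ±2-day windows at each end. Intervals between earlier draws from Day 1 are 7, 7, 14, 14, 14 and 28 days, so the longest on treatment is 28 (Day 57 to Day 85).

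**3. Pairing in Part B.** Biomarker days are 1, 29, 57, 85 and 106 (5 draws, matching Table 7-3). Chemistry is drawn at the same visit on Days 1, 29, 57 and 85. Only Day 106 is unpaired.

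**4. Residual drug.** With simple exponential decline, the fraction of the Day 78 level is 2^(−(day − 78)/half-life):

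| Day | Days after Dose 12 | Half-life 7 days | Half-life 14 days |
|---|---|---|---|
| 85 | 7 | 50% | 71% |
| 106 | 28 | 6.3% | 25% |
| 134 | 56 | 0.4% | 6.3% |
| 162 | 84 | 0.02% | 1.6% |

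By the usual five-half-life convention (an assumption, not in the documents), washout ends near Day 78 + 35 = 113 or Day 78 + 70 = 148. Exposure thus covers part of the gap, not all of it.

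**5. Usual onset window.** 4 to 14 days after Day 78 is Days 82 to 92. Day 85 is the only scheduled chemistry draw in it.

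**6. Reporting.** SAP 10.4.4 expressly brings unscheduled readings into the QTc outlier analysis. SAP 10.4.2 has no such exception, so the general rule in 10.1.2 applies. For example, a for-cause ALT of 6x ULN on Day 100 would be listed but would not enter the liver tables.

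**The case against.** The case for leaving the schedule alone is respectable. Nothing in the protocol promises transaminases on Day 106. Section 7 allows extra safety laboratory tests when clinically indicated. Under its Throughout the Study heading, it also requires a clinically significant abnormality in need of monitoring to be followed until it resolves or is stable. Day 85 is well placed: 7 days after Dose 12 and 14 days after Dose 11, inside the usual onset window for both. Day 106 is 28 days after the last dose and outside that window. Section 2 describes the type 2 rises without associated bilirubin or ALP increases, and the 18x ULN value fell below ULN with continued dosing.

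Much of this stands, and it rules out several stronger readings:
- A reader might infer that a raised ALT on Day 85 need not be rechecked for 11 weeks. The follow-up rule contradicts that for clinically significant rises. What is absent is a scheduled recheck.
- A reader might infer that the Day 106 biomarkers are uninterpretable, or were added to explain ALT. The protocol calls them an additional safety assessment and gives no such purpose. They can be compared with baseline, placebo, same-day drug concentration and the four earlier paired draws.
- Section 2 also says "With repeated weekly dosing, substantial (10-30x) accumulation of REMD-477 is expected". A reader might multiply this by the residual fractions and conclude that levels above a first dose persist for 4 to 8 weeks. But the accumulation figures come from the type 2 study, with its 1-week half-life, while the 2-week half-life comes from single doses in healthy volunteers. Linear accumulation at these half-lives would be only 1/(1 − 2^(−7/7)) = 2.0 to 1/(1 − 2^(−7/14)) = 3.4, so the inputs do not fit one simple model.
- The ALT rise at 21 and 49 days in R477-101 was one subject on blinded treatment, below 1.6x ULN, with timing the protocol itself calls inconsistent with earlier observations. It is weak evidence of a late effect.

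The objection does not answer two things. Discretionary testing needs a reason to test, which a symptom-free new rise does not supply. And values obtained that way are left out of the SAP summaries.

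**Conclusion.** The point holds as a gap in scheduled measurement and a mismatch between two schedules in Part B. It does not show that subjects with known abnormalities go unfollowed. In both Parts no scheduled liver chemistry falls in the 77 days between Day 85 and Week 24, at 0 of 2 intervening visits. In Part B, 1 of 5 liver-biomarker draws cannot be related to same-visit ALT or AST. A symptom-free rise that begins after Day 85 has no scheduled detection until Week 24, and the summaries cannot describe recovery between those visits.

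The counts rest on Appendix A and agree with the blood-volume tables. The 6% to 25% residual on Day 106 rests on exponential decline and is indicative only; the planned Day 106 concentration sample makes the same case without a model. A Day 106 draw would inform on recovery and later rises and would pair the biomarkers. It would not cover the rest of the Day 82 to 92 window.

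**What to change.** Reconcile the chemistry row of Appendix A with the liver-biomarker schedule so that the Day 106 visit carries ALT, AST, ALP, and total and direct bilirubin in both Parts. Add Day 106 to the by-timepoint ALT, AST and bilirubin tables in SAP 10.4.2. Whether Day 134 also needs chemistry is for the sponsor to decide.

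The cost is one mark in each Schedule, the matching count in the blood-volume tables (9 to 10) and about 5 mL per subject. Against the 380.5 mL of Table 7-3 that is 5/380.5 = 1.3%. Blood is already drawn on Day 106 in both Parts for drug concentration and for insulin, C-peptide, GLP-1 and glucagon, so no new visit is needed.

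It would also help if SAP 10.4.2 said whether unscheduled post-dose values count toward the maximum ALT and AST. If sampling is already complete, report the gap as a limitation in the study report.
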